### 8.3.2 Reasons for Removal From Study

Reasons for removal of a subject from the study are:

- decision by sponsor
- withdrawal of consent from study
- death
- lost to follow-up

Approved

As part of the study, sites may be asked to conduct searches of public records, such as those establishing survival status, if available, to obtain survival data for any subject for whom the survival status is not known.

## 9. SAFETY DATA COLLECTION, RECORDING, AND REPORTING

### 9.1 Definition of Safety Events

#### 9.1.1 Disease Related Events

Disease Related Events are events (serious or non-serious) anticipated to occur in the study population due to the underlying disease eg, disease progression (Table 9). Such events do not meet the definition of an adverse event unless assessed to be more severe than expected for the subject's condition.

Disease Related Events that do not qualify as Adverse Events or Serious Adverse Events:

- An event which is part of the normal course of disease under study (eg, disease progression in oncology or hospitalization due to disease progression) is to be reported as a Disease Related Event.
- Death due to the disease under study is to be recorded on the event CRF.

If the outcome of the underlying disease is worse than that which would normally be expected for the subject, or if the investigator believes there is a causal relationship between the IP(s)/study treatment protocol required therapies and disease worsening, this must be reported as an adverse event or a serious adverse event. Table 9 outlines the expected Disease-Related Events by System Organ Class.

**Table 9. Disease-related Adverse Events by System Organ Class**

System Organ Class	Preferred Terms
Blood and lymphatic system disorders	lymphadenopathy
General disorders and administration site conditions	Disease progression fatigue
Investigations	Weight decreased
Skin and subcutaneous tissue disorders	Night sweats

Approved

Disease Related Events that would qualify as an Adverse Event or Serious Adverse Event:

- An event based on the underlying disease that is worse than expected as assessed by the investigator for the subject's condition or if the investigator believes there is a causal relationship between the investigational product(s)/study treatment/protocol-required therapies and disease worsening, this must be reported as an Adverse Event or Serious Adverse Event.

### 9.1.2 Adverse Events

An adverse event is defined as any untoward medical occurrence in a clinical trial subject. The event does not necessarily have a causal relationship with study treatment. The investigator is responsible for ensuring that any adverse events observed by the investigator or reported by the subject are recorded in the subject's medical record.

The definition of adverse events includes worsening of a pre-existing medical condition. Worsening indicates that the pre-existing medical condition or underlying disease (eg, diabetes, migraine headaches, gout) has increased in severity, frequency, and/or duration more than would be expected, and/or has an association with a significantly worse outcome than expected. A pre-existing condition that has not worsened more than anticipated (ie, more than usual fluctuation of disease) during the study or involves an intervention such as elective cosmetic surgery or a medical procedure while on study, is not considered an adverse event.

If the severity of an adverse event changes from the date of onset to the date of resolution, record as a single event with the worst severity on the Event CRF.

For situations when an adverse event or serious adverse event is due to the underlying lymphoma, report all known signs and symptoms. Death due to disease progression in the absence of signs and symptoms should be reported as the primary tumor type (eg, relapsed/refractory indolent NHL).

Note: The term "disease progression" should not be used to describe the disease related event or adverse event.

An adverse device effect is any adverse event related to the use of a medical device. Adverse device effects include adverse events resulting from insufficient or inadequate instructions for use, adverse events resulting from any malfunction of the device, or adverse events resulting from use error or from intentional misuse of the device.

The investigator's clinical judgment is used to determine whether a subject is to be removed from treatment due to an adverse event. In the event a subject, or subject's

legally acceptable representative requests to withdraw from protocol-required therapies or the study due to an adverse event, refer to [Section 8.1](#) for additional instructions on the procedures recommended for safe withdrawal from protocol-required therapies or the study.

### 9.1.3 Serious Adverse Events

A serious adverse event is defined as an adverse event that meets at least 1 of the following serious criteria (unless it meets the definition of a Disease Related Event as defined in [Section 9.1.1](#)):

- fatal
- life threatening (places the subject at immediate risk of death)
- requires in-patient hospitalization or prolongation of existing hospitalization
- results in persistent or significant disability/incapacity
- congenital anomaly/birth defect
- other medically important serious event

A disease related event blood and lymphatic system disorders or investigations are to be reported as a serious adverse event if:

- the subject's pre-existing condition becomes worse than what the investigator would consider typical for a patient with the same underlying condition, or
- if the investigator believes a causal relationship exists between the investigational medicinal product(s)/protocol-required therapies and the event,
- and the event meets at least 1 of the serious criteria.

An adverse event would meet the criterion of "requires hospitalization", if the event necessitated an admission to a health care facility (eg, overnight stay).

If an investigator considers an event to be clinically important, but it does not meet any of the serious criteria, the event could be classified as a serious adverse event under the criterion of "other medically important serious event". Examples of such events could include allergic bronchospasm, convulsions, blood dyscrasias, DILI (see [Appendix D](#) for drug-induced liver injury reporting criteria), or events that necessitate an emergency room visit, outpatient surgery, or urgent intervention.

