## 9.2 Safety Event Reporting Procedures

### 9.2.1 Reporting Procedures for Disease Related Events

The investigator is responsible for ensuring that all Disease Related Events observed by the investigator or reported by the subject that occur after the first dose of investigational

medicinal product(s)/study treatment/protocol-required therapies through the safety follow-up visit and are recorded on the Event CRF as a Disease Related Event.

Disease Related Events assessed by the investigator to be more severe than expected and/or related to the investigational medicinal product(s)/study treatment/protocol-required therapies, and determined to be serious, must be recorded on the Event eCRF as Serious Adverse Events.

Additionally, the investigator is required to report a fatal Disease Related Event on the Event eCRF.

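### Protocol 9.1.3 readmits disease related events as SAEs in only two of Table 9's four organ classes, in conflict with 9.1.1 and 9.2.1, so serious fatigue or night sweats could miss 24-hour SAE submission

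*Protocol*

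**What the plan says.** Protocol 9.1.3 defines a serious adverse event by the usual seriousness criteria but carves out disease related events: "unless it meets the definition of a Disease Related Event as defined in" Section 9.1.1. It then gives its own re-entry rule: "A disease related event blood and lymphatic system disorders or investigations are to be reported as a serious adverse event if" the condition is worse than typical or a causal link to treatment is suspected, "and the event meets at least 1 of the serious criteria".

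Table 9 lists the expected disease related events in four system organ classes:

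- "Blood and lymphatic system disorders": lymphadenopathy
- "General disorders and administration site conditions": disease progression and fatigue
- Investigations: "Weight decreased"
- Skin and subcutaneous tissue disorders: night sweats

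Three other places set no organ-class limit. Under 9.1.1, if the outcome is worse than expected or treatment is thought to have caused disease worsening, "this must be reported as an adverse event or a serious adverse event". The text beneath Table 9 repeats this. Section 9.2.1 says that disease related events that are more severe than expected and/or related to treatment, and serious, "must be recorded on the Event eCRF as Serious Adverse Events".

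The 24-hour submission duty is in 9.2.2.2 and attaches to serious adverse events. Section 9.2.1 sets no time limit for an event that stays classified as a disease related event.

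**The concern.** The section that defines a serious adverse event and the section that tells sites how to report disease related events give different answers for the same event. Take serious fatigue that a site has recorded as a disease related event and judges related to blinatumomab. Under 9.2.1 it must be recorded as an SAE. Under 9.1.3 it is removed by the carve-out, and the re-entry rule does not name its organ class.

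At stake is whether the sponsor hears of the event within 24 hours, and whether sites classify like events alike. Adverse events form part of the primary endpoint, this is the first subcutaneous use of blinatumomab in humans, and about 15 to 20 sites in the United States, Europe and Australia would apply the text.

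**Working it through.** No design calculation bears on this point, and the plan gives no figure to reproduce. The check is a comparison of scope.

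**Step 1. Organ classes covered by each upgrade rule.**

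| Table 9 class | Terms | 9.1.1 and text under Table 9 | 9.1.3 | 9.2.1 |
|---|---|---|---|---|
| Blood and lymphatic | lymphadenopathy | yes | yes | yes |
| General disorders | disease progression, fatigue | yes | not named | yes |
| Investigations | weight decreased | yes | yes | yes |
| Skin | night sweats | yes | not named | yes |

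Classes: 9.1.1 covers 4 of 4, 9.2.1 covers 4 of 4, 9.1.3 covers 2 of 4.

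Terms: 1 + 2 + 1 + 1 = 5 in all. Section 9.1.3 covers 1 + 1 = 2, leaving 5 − 2 = 3 (disease progression, fatigue, night sweats).

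**Step 2. What the gap amounts to in practice.** Section 9.1.2 says the term disease progression should not be used to describe a disease related event or an adverse event. That leaves 3 − 1 = 2 usable terms: fatigue and night sweats.

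**Step 3. Does 9.1.3 really exclude the other two classes?** The word only does not appear. The exclusion follows from the structure: all disease related events are taken out by the carve-out, then two named classes are put back. If all four were meant, naming two would serve no purpose. Neither document explains why these two classes should differ.

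**Step 4. Do the triggers match once class is set aside?** They do not.

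- 9.1.1 and the text under Table 9 ask whether treatment caused *disease worsening*.
- 9.1.3 asks whether treatment caused *the event*.
- 9.2.1 asks whether the event is more severe than expected and/or related to treatment.

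Fatigue thought to be caused by blinatumomab, without worsening lymphoma, does not clearly meet the causal test in 9.1.1. Its status then depends on 9.1.3 and 9.2.1, the two sections that disagree on class.

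**Step 5. What happens to an event left as a disease related event?** Under 9.2.1 it is still recorded on the Event CRF. SAP 10.5.1 lists tables of treatment emergent, serious treatment emergent, treatment related, serious treatment related and fatal events, and says these tables include disease related events. SAP Section 6 repeats the unrestricted 9.1.1 wording and the same four classes, so it does not settle the conflict in the protocol. What the event can lose is SAE status and, with it, the 24-hour submission under 9.2.2.2.

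**The case against.** The strongest reply is that 9.2.1 is the operative reporting procedure, is mandatory and covers every class. An event is missed only if a site prefers an exclusion inferred from 9.1.3 to an express requirement in 9.2.1. This stands as a limit: omission is a risk, not a certainty. It does not remove the conflict, because 9.1.3 is where a site looks to decide what an SAE is, and neither section is said to prevail.

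A second reply is that the carve-out points to 9.1.1, which itself separates disease related events that qualify as adverse events from those that do not, so an upgraded event was never carved out. That reading is available, but it leaves the two-class sentence with nothing to do.

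A third is that fatigue attributed to blinatumomab is not due to the underlying disease, so it is an ordinary adverse event from the start. An investigator could take that view. But Table 9 lists fatigue by name, and 9.2.1 expressly provides for disease related events that are related to treatment.

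A reader might go further and infer that such an event drops out of the SAE count, so that one misclassified event would move SAE incidence by 1/6 = 16.7 points in a Period 1 cohort or 1/15 = 6.7 points in Period 2. The documents do not support this. SAP 10.5.1 includes disease related events in the tables, the serious ones among them. The denominators would also be wrong: 6 and 15 count evaluable subjects, whereas safety is analysed on all subjects who receive blinatumomab.

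**Conclusion.** The point holds as an internal inconsistency. Section 9.1.3 gives a narrower rule than 9.1.1, the text under Table 9 and 9.2.1, by 2 of 4 organ classes and 3 of 5 listed terms, and in practical effect by fatigue and night sweats. A site relying on 9.1.3 could leave a serious event of either kind, judged related or worse than expected, as a disease related event and not submit it as an SAE within 24 hours, although 9.2.1 requires SAE recording.

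The harm is to SAE classification and expedited reporting. No loss from the safety tables is shown, and no percentage-point effect should be attached. The conclusion assumes that the site treats the event as a disease related event in the first place and follows 9.1.3 rather than 9.2.1. How often that would happen cannot be estimated from the documents. The statement about the tables rests on SAP 10.5.1 being applied as written, with seriousness captured for disease related events on the Event CRF.

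**What to change.** In Protocol 9.1.3, replace the two named classes in the opening of the re-entry rule with *any disease related event (Table 9, all system organ classes)*, and leave the seriousness condition as it stands.

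Widening the class list alone would not give one rule. Also align the causality trigger across 9.1.1 (with the text under Table 9), 9.1.3 and 9.2.1, so that all three refer either to relatedness of the event or to relatedness of disease worsening. If the wording of 9.1.1 changes, carry the change into SAP Section 6, which repeats it.

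The cost is one sentence in 9.1.3 plus matching edits to the trigger wording. No treatment rule or analysis method changes. At most, a few more events would be submitted as SAEs.

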## 9.2 Safety Event Reporting Procedures

### 9.2.1 Reporting Procedures for Disease Related Events

The investigator is responsible for ensuring that all Disease Related Events observed by the investigator or reported by the subject that occur after the first dose of investigational

medicinal product(s)/study treatment/protocol-required therapies through the safety follow-up visit and are recorded on the Event CRF as a Disease Related Event.

Disease Related Events assessed by the investigator to be more severe than expected and/or related to the investigational medicinal product(s)/study treatment/protocol-required therapies, and determined to be serious, must be recorded on the Event eCRF as Serious Adverse Events.

Additionally, the investigator is required to report a fatal Disease Related Event on the Event eCRF.

## **9.2.2 Adverse Events**

### **9.2.2.1 Reporting Procedures for Adverse Events That do not Meet Serious Criteria**

The investigator is responsible for ensuring that all adverse events observed by the investigator or reported by the subject that occur after first dose of IP through 30 days after the last dose of study treatment or the safety follow-up visit (whichever is later) are reported using the Event CRF.

The investigator must assign the following adverse event attributes:

- Adverse event diagnosis or syndrome(s), if known (if not known, signs or symptoms),
- Dates of onset and resolution (if resolved),
- Severity [and/or toxicity per protocol],
- Assessment of relatedness to blinatumomab or protocol required medication or medical device, and
- Action taken.

If the severity of an adverse event changes from the date of onset to the date of resolution, record as a single event with the worst severity on the Adverse Event Summary CRF.

The adverse event grading scale used will be the Amgen adverse event standard grading score; CTCAE. The grading scale used in this study is described in [Appendix D](#).

The investigator must assess whether the adverse event is possibly related to blinatumomab. This relationship is indicated by a “yes” or “no” response to the question: Is there a reasonable possibility that the event may have been caused by the Investigational Medicinal Product?

The investigator must assess whether the adverse event is possibly related to any study-mandated activity (eg, administration of investigational product, protocol-required therapies, device(s) and/or procedure (including any screening procedure(s))). This relationship is indicated by a “yes” or “no” response to the question: “Is there a reasonable possibility that the event may have been caused by a study activity (eg, administration of investigational product, protocol-required therapies, device(s)), and/or procedure”?

The investigator is responsible for reviewing laboratory test results and determining whether an abnormal value in an individual study subject represents a change from the subject’s baseline values. Laboratory value changes that require intervention (eg, treatment, hospitalization, or adjustment in current therapy) should be recorded as adverse events. In addition, if signs or symptoms are associated with a laboratory abnormality, the signs/symptoms and the laboratory abnormality should all be recorded as adverse events. The laboratory abnormality and any signs/symptoms should be graded according to their own CTCAE criteria.

#### **9.2.2.2 Reporting Procedures for Serious Adverse Events**

The investigator is responsible for ensuring that all serious adverse events observed by the investigator or reported by the subject that occur after signing of the informed consent through the safety follow-up period 30 days after the last dose of protocol-specified therapies are recorded in the subject’s medical record and are submitted to Amgen. All serious adverse events must be submitted to Amgen within 24 hours following the investigator’s knowledge of the event via the Event CRF.

If the electronic data capture (EDC) system is unavailable to the site staff to report the serious adverse event, the information is to be reported to Amgen via an electronic Serious Adverse Event (eSAE) Contingency Report Form within 24 hours of the investigator’s knowledge of the event. See [Appendix F](#) for a sample of the Serious Adverse Event Worksheet/eSAE Contingency Report Form.

The investigator must assess whether the serious adverse event is possibly related to the blinatumomab. This relationship is indicated by a “yes” or “no” response to the question: Is there a reasonable possibility that the event may have been caused by blinatumomab?

The investigator is expected to follow reported serious adverse events until stabilization or reversibility.

Approved

New information relating to a previously reported serious adverse event must be submitted to Amgen. All new information for serious adverse events must be sent to Amgen within 24 hours following knowledge of the new information. If specifically requested, the investigator may need to provide additional follow-up information, such as discharge summaries, medical records, or extracts from the medical records. Information provided about the serious adverse event must be consistent with that recorded on the Event CRF.

If a subject is permanently withdrawn from protocol-required therapies because of a serious adverse event, this information must be submitted to Amgen.

Amgen will report serious adverse events and/or suspected unexpected serious adverse reactions as required to regulatory authorities, investigators/institutions, and IRBs/IECs in compliance with all reporting requirements according to local regulations and good clinical practice.

The investigator is to notify the appropriate IRB/IEC of serious adverse events occurring at the site and other adverse event reports received from Amgen, in accordance with local regulatory requirements and procedures.

#### **9.2.2.3 Reporting Serious Adverse Events After the Protocol-required Reporting Period**

There is no requirement to monitor study subjects for serious adverse events following the protocol-required reporting period or after end of study. However, these serious adverse events can be reported to Amgen. In some countries (eg, European Union member states), investigators are required to report serious adverse events that they become aware of after end of study. If serious adverse events are reported, the investigator is to report them to Amgen within 24 hours following the investigator's knowledge of the event.

Serious adverse events reported outside of the protocol-required reporting period will be captured within the safety database as clinical trial cases for the purposes of expedited reporting.

#### **9.3 Pregnancy and Lactation Reporting**

If a female subject becomes pregnant, or a male subject fathers a child, while the subject is taking blinatumomab report the pregnancy to Amgen Global Patient Safety as specified below.

In addition to reporting any pregnancies occurring during the study, investigators should monitor for pregnancies that occur after the last dose of blinatumomab through 48 hours after the last dose of cIV blinatumomab or **96** hours after the last dose of SC blinatumomab for both male and female subjects.

The pregnancy should be reported to Amgen Global Patient Safety within 24 hours of the investigator's knowledge of the event of a pregnancy. Report a pregnancy on the Pregnancy Notification Worksheet ([Appendix G](#)). Amgen Global Patient Safety will follow-up with the investigator regarding additional information that may be requested.

If a female subject becomes pregnant during the study, the investigator should attempt to obtain information regarding the birth outcome and health of the infant. If a male subject's female partner becomes pregnant, the investigator should discuss obtaining information regarding the birth outcome and health of the infant from the pregnant partner.

If the outcome of the pregnancy meets a criterion for immediate classification as a Serious Adverse Event (eg, female subject experiences a spontaneous abortion, stillbirth, or neonatal death or there is a fetal or neonatal congenital anomaly) the investigator will report the event as a Serious Adverse Event.

If a female breastfeeds while taking protocol-required therapies report the lactation case to Amgen as specified below.

In addition to reporting a lactation case during the study, investigators should report lactation cases that occur 48 hours after the last dose of cIV blinatumomab or **96** hours after the last dose of SC blinatumomab.

Any lactation case should be reported to Amgen Global Patient Safety within 24 hours of the investigator's knowledge of event. Report a lactation case on the Lactation Notification Worksheet ([Appendix G](#)). Amgen Global Patient Safety will follow-up with the investigator regarding additional information that may be requested.

